7.8.2 Secondary Efficacy Endpoint(s)

7.8.2.1 PBAC Score

Analysis Set: Full Analysis Set

Analysis

Variable(s): Proportion of subjects with a total PBAC score of < 10 from Week 2 to 6
Proportion of subjects with a total PBAC score of < 10 from Week 18 to 24
Proportion of subjects with a total PBAC score of < 10 for 6 weeks before the final dose of study drug

Analytical

Method(s): For each variable, frequency will be summarized by treatment group. The point estimate and 2-sided 95% confidence interval of the difference in the percentage will be calculated between TAK-385 40 mg group and leuprorelin group, using FM method with the non-inferiority margin of -15%. The confidence interval will be presented in a descriptive manner and not for the purpose of statistical inference.

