4.0 INTRODUCTION

4.1 Background

Uterine fibroid is a benign sex hormone-dependent gynecological disease affecting 1 in every 3 to 4 women. Most uterine fibroids are asymptomatic, but clinical symptoms such as increase in menstrual blood loss and anemia due to menorrhagia as well as compression and pain in the bladder and pelvis due to large myoma are seen in about 10% to 20% of patients. In particular, menorrhagia is considered to be caused by the combination of an increase in surface area of the uterine cavity; poor uterine contraction due to myoma; and increased circulation, congestion, or impaired hemostasis due to hypertrophy of the endometrium in the vicinity of the myoma. Persistent menorrhagia is known to induce iron-deficiency anemia. Therefore, menorrhagia is a primary factor that deteriorates the quality of life (QOL) of patients with uterine fibroids.

Gonadotropin-releasing hormone (GnRH) agonists, such as leuprorelin are commonly used for the treatment of benign sex hormone-dependent gynecological diseases, such as endometriosis and uterine fibroids. It is considered that continuous use of a GnRH agonist induces a transient increase in the secretion of gonadotropins (flare up), followed by pituitary and gonadal desensitization that decreases sex hormone secretion. Therefore, GnRH agonists exert therapeutic effects against these diseases by reducing secretion of sex hormones. However, GnRH agonists often cause flare up (temporary worsening of symptoms) and may typically take about 3 to 4 weeks before therapeutic effects begin to emerge. They also cannot be orally administered because they are peptides. For these reasons, the development of a new oral drug that is not associated with temporal worsening of symptoms is awaited for the treatment of these diseases.

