13.1.3 Efficacy Analysis

(1) Primary endpoint and analytical methods

Primary endpoint

Proportion of subjects with a total PBAC score of < 10 from Week 6 to 12

Primary analysis

The following analyses will be performed based on the FAS:

The proportion of subjects with a total PBAC score of < 10 from Week 6 to 12 will be summarized by treatment group. The point estimate and 2-sided 95% confidence interval of the difference in the percentage will be calculated between TAK-385 40 mg group and leuprorelin group (TAK-385 40 mg group – leuprorelin group). In addition, non-inferiority test using Farrington and Manning method with a non-inferiority margin of 15% will be conducted for the comparison between TAK-385 40 mg and leuprorelin group.

Secondary analysis

An analysis similar to the above “Primary analysis” will be performed using the PPS to assess the robustness of the results (sensitivity analysis).

(2) Secondary endpoints and analytical methods

Secondary endpoints

- Proportion of subjects with a total PBAC score of < 10 (from Week 2 to 6, from Week 18 to 24, and for 6 weeks before the final dose of study drug)
- Myoma volumes (Week 2, 4, 8, 12 and 24)
- Uterine volumes (Week 2, 4, 8, 12 and 24)
- HGB (Week 4, 8, 12, 16, 20, 24 and Follow-up)
- NRS score (from Week 6 to 12, from Week 2 to 6, from Week 18 to 24, and for 6 weeks before the final dose)
- UFS-QOL score (Week 4, 8, 12, 16, 20, 24 and Follow-up)

Analytical methods

1. Proportion of subjects with a total PBAC score of < 10

Frequency will be summarized by treatment group. The point estimate and 2-sided 95% confidence interval of the difference in the percentage will be calculated between TAK-385 40 mg group and leuprorelin group.

2. Myoma and uterine volumes, HGB, NRS score and UFS-QOL scores

For each variable, summary statistics will be provided by treatment group for each visit. Two-sided 95% confidence interval of the difference will be calculated between TAK-385 40 mg and leuprorelin group.

(3) Additional efficacy endpoints

Additional endpoints

- HCT, serum Fe, and serum ferritin (Week 4, 8, 12, 16, 20, 24 and Follow-up)
- Use of analgesic medications during the Treatment (from Week 6 to 12, from Week 2 to 6, from Week 18 to 24, and for 6 weeks before the final dose)
- WPAI:GH during the Treatment (Week 2, 4, 8, 12 and 24)

(4) Methods of data transformation and handling of missing data

Details will be described in the SAP.

(5) Significance level and confidence coefficient

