6.0 DETERMINATION OF SAMPLE SIZE

Justification of Sample size

In a clinical study of ulipristal acetate (already approved in Europe) compared with leuprorelin conducted overseas, the proportion of subjects with a total PBAC score of < 75 for 28 days before Week 13 was 89.1% in the TAP-144-SR (1M) 3.75 mg group, and the proportion of subjects with a total PBAC score of ≤ 2 for 28 days before Week 13 was 80.4%.

In TAK-385 phase 2 study in the treatment of uterine fibroids, the point estimate (and corresponding 2-sided 95% confidence interval) of the proportion of subjects with a total PBAC score of < 10 from Week 6 to 12 was 83.6% (71.2%, 92.2%) in the TAK-385 40 mg group.

Based on the results of the above 2 studies, the proportions of subjects with a total PBAC score of < 10 from Week 6 to 12 in both TAK-385 40 mg group and leuprorelin group are estimated to be 83.6%.

Under this assumption, a sample size of at least 129 subjects per group will provide $\geq 90\%$ power to demonstrate non-inferiority at 1-sided 0.025 level of significance, using a non-inferiority margin of 15% (nQuery Advisor 6.01).

Based on the above, a sample size of 129 subjects per group (258 subjects in total) is planned as the number of evaluable subjects. Assuming that approximately 10% of subjects will not be evaluable for the primary endpoint, 144 subjects are to be randomized to each group, for a total of 288 subjects.

Justification of non-inferiority margin

As the result of the TAK-385 phase 2 study in the treatment of uterine fibroids, the point estimate (and corresponding 2-sided 95% confidence interval) of the difference in the proportion of subjects with a total PBAC score of < 10 from Week 6 to 12 was 83.6% (73.9%, 93.4%) between the TAK-385 40 mg group and Placebo group. Assuming that leuprorelin has comparable effect to TAK-385 40 mg, the non-inferiority margin of 15% is considered smaller than the smallest effect size that leuprorelin would be reliably expected to have.

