7.0 METHODS OF ANALYSIS AND PRESENTATION

7.1 General Principles

All statistical analyses will be conducted using SAS® Version 9.2, or higher.

A statistical test for the primary endpoint will be reported as 1-sided and will be assessed at $\alpha=0.025$ significance level and all confidence intervals will be reported as 2-sided unless otherwise stated. P-values will be rounded to 4 decimal places prior to assessment of statistical significance.

Means and medians will be presented to 1 more decimal place than the recorded data. The standard deviations (SDs) will be presented to 2 more decimal places than the recorded data. Confidence intervals about a parameter estimate will be presented using the same number of decimal places as the parameter estimate.

Where appropriate, variables will be summarized descriptively by study visit. For the categorical variables, the count and proportions of each possible value will be tabulated by treatment group. The denominator for the proportion will be based on the number of subjects who provided non-missing responses to the categorical variable. For continuous variables, the number of subjects with non-missing values, mean, median, SD, minimum, and maximum values will be tabulated. Confidence intervals for continuous variables will be calculated based on t-statistics and ones for categorical variables will be based on Wald confidence intervals without using any model, unless otherwise stated.

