7.8.3.4 Amenorrhea (The subject with a total PBAC score of 0)

Analysis Set: Full Analysis Set

Analysis

Variable(s): Proportion of subjects with a total PBAC score of 0 from Week 6 to 12
Proportion of subjects with a total PBAC score of 0 from Week 2 to 6
Proportion of subjects with a total PBAC score of 0 from Week 18 to 24
Proportion of subjects with a total PBAC score of 0 for 6 weeks before the final dose of study drug

Analytical

Method(s): For each variable, frequency will be summarized by treatment group.
The point estimate and 2-sided 95% confidence interval of the difference in the percentage will be calculated between TAK-385 40 mg group and leuprorelin group, using FM method with the non-inferiority margin of -15%. The confidence interval will be presented in a descriptive manner and not for the purpose of statistical inference.

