7.13 Changes in the Statistical Analysis Plan

Change from previous version are described in following table.

Page	Previous version	Current version	Reason
14	7.1.1 Study Definitions	7.1.1 Study Definitions Oral iron preparation The drug with the following drug code of WHODD: 00023503001, 00023505001, 00023520001, 00023550009, 00023550074, 90059601001	Specify the definition of Oral iron preparation based on blind review
17	7.1.4 Methods for Handling Missing Data	7.1.4 Methods for Handling Missing Data · For LH, FSH, E2, P and clinical laboratory tests, values less than the lower limit of quantification will be treated as zero when calculating the descriptive statistics.	Specify how to deal with value with lower limit of quantification for LH, FSH, E2, P and clinical laboratory

23	7.4Demographic and Other Baseline Characteristics Other Medicines for UterineFibroids	7.4Demographic and Other Baseline Characteristics Other Medicines for Uterine Fibroids	Typo
26	7.8.1.1Primary Analysis If the lower bound of the 95%CI is greater or equal to the non-inferiority margin of 15%,, then non-inferiority of TAK-385 40mg to leuprorelin will be concluded.	7.8.1.1Primary Analysis If the lower bound of the 95%CI is greater or equal to the non-inferiority margin of -15% ,, then non-inferiority of TAK-385 40mg to leuprorelin will be concluded.	Typo
27	7.8.1.4Examination of Subgroups Cervical Fibroid[Yes, No]	7.8.1.4Examination of Subgroups removed	Removed based on blind review
28	7.8.2.1PBAC Score For each variable, frequency will be summarized by treatment group. The point estimate and 2-sided 95% confidence interval of the difference in the percentage will be calculated between TAK-385 40 mg group and leuprorelin group, using FM method.	7.8.2.1PBAC Score For each variable, frequency will be summarized by treatment group. The point estimate and 2-sided 95% confidence interval of the difference in the percentage will be calculated between TAK-385 40 mg group and leuprorelin group, using FM method with the non-inferiority margin of -15%. The confidence interval will be presented in a descriptive manner and not for the purpose of statistical inference.	Specify the detail description how to calculate CI using FM method, based on the comment.
29	7.8.2.3Hemoglobin	7.8.2.3Hemoglobin HGB at Baseline (g/dL)[Min<= - <12, 12<= - <=Max]	Added based on blind review
32		Section 7.8.3.4 was newly added.	Added based on the comment.

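### Descriptive intervals for the secondary PBAC windows and amenorrhea appear to take their standard error from a -15 point difference that is not tested there, so they widen beyond 95% as rates near 0 or 1 or the difference moves away from -15

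*SAP*

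**What the plan says.** SAP 7.8.2.1 covers the proportion with a total PBAC score below 10 in Weeks 2 to 6, in Weeks 18 to 24, and in the six weeks before the final dose. It asks for a two-sided 95% interval for the difference "using FM method with the non-inferiority margin of -15" percent. SAP 7.8.3.4 uses the same construction, "using FM method with the non-inferiority margin of" -15%, for a total score of 0 in four windows. Section 7.8.2.1 adds: "The confidence interval will be presented in a descriptive manner and not for the purpose of statistical inference". Section 7.8.3.4 carries the same restriction.

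The change table in SAP 7.13 gives the reason for the wording in 7.8.2.1: "Specify the detail description how to calculate CI using FM method".

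Nothing else in the documents sets a -15 point hypothesis for these endpoints. SAP 7.1 mentions testing for one endpoint: "A statistical test for the primary endpoint will be reported as 1-sided". For the secondary PBAC proportions, Protocol 13.1.3 plans "Frequency will be summarized by treatment group. The point estimate and 2-sided 95% confidence interval of the difference in the percentage", with no margin. The FM non-inferiority test is in SAP 7.8.1.1, for Weeks 6 to 12.

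**The concern.** A non-inferiority margin belongs in a test. In a standalone interval it has a place only if the standard error is evaluated at that null. A standard error that is right for a true difference of -15 points need not be right for a difference of 0 or of +10.

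These intervals are the only planned between-arm statement of precision for seven outputs, and readers will take them as 95% intervals. The documents give no expected rates for these windows or for amenorrhea, so it cannot be assumed that the results will fall where the construction works well. There is also some reason to expect differences above zero early on. Protocol 4.1 says that GnRH agonists "may typically take about 3 to 4 weeks before therapeutic effects begin to emerge" and that TAK-385 acts faster. At stake is the accuracy of the error bars. No claim rests on them.

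**Working it through.** **Inputs.** SAP 6.0 plans 129 evaluable and 144 randomized per arm, with 83.6% response in both arms. The phase 2 result for Weeks 6 to 12 "was 83.6% (71.2%, 92.2%) in the TAK-385 40 mg group". The overseas study cited there had 80.4% of leuprorelin subjects at a PBAC score of 2 or less. All other rates below are assumed, to show the range.

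**The plan's own figure.** With unpooled variance, n = (1.96 + 1.2816)² × 2 × 0.836 × 0.164 / 0.15² = 128.05, so 129 per arm. Then 129 / 0.9 = 143.3, so 144. Both match SAP 6.0.

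**Two readings of the interval.** Let x1 and x2 be the responders on TAK-385 and leuprorelin, n the size of each arm, and d = (x1 - x2)/n.

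- Fixed null: d ± 1.96 × √[p̃1(1-p̃1)/n + p̃2(1-p̃2)/n], where p̃1 and p̃2 maximise the likelihood subject to p̃1 - p̃2 = -0.15.
- Inverted FM test: all values δ for which |d - δ| / SE(δ) ≤ 1.96, with the constraint p̃1 - p̃2 = δ re-solved at each δ.

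In the second the margin plays no part and the phrase would be redundant. SAP 7.13 says that the wording specifies the calculation, which supports the first. This is an inference, since no formula is given.

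**Two examples at n = 129.**

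- 108 responders in each arm (83.7%): p̃1 = 0.7381 and p̃2 = 0.8881. SE = √[(0.1933 + 0.0994)/129] = 0.0476, so the half-width is 9.3 points. The inverted interval gives 9.2 and Wald 9.0.
- 119 responders in each arm (92.2%): p̃1 = 0.8048 and p̃2 = 0.9548. SE = √[(0.1571 + 0.0432)/129] = 0.0394, so the half-width is 7.7 points. The inverted interval gives 6.9 and Wald 6.5.

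In the second example the constraint pulls one arm down to about 80%, where binomial variance is larger than at the observed 92%. That is the source of the extra width.

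**Exact coverage.** Summed over all 130 × 130 outcomes at n = 129 per arm. Width is the mean width of the fixed-null interval relative to Wald.

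| True rates, TAK-385 / leuprorelin (%) | Coverage, fixed at -15 | Width vs Wald |
|---|---|---|
| 71.2 / 71.2 | 94.9% | 0% |
| 83.6 / 83.6 (planned) | 95.7% | +4% |
| 83.6 / 80.4 | 95.7% | +4% |
| 88.6 / 83.6 (88.6 assumed) | 96.5% | +8% |
| 92.2 / 83.6 | 97.3% | +13% |
| 83.6 / 92.2 | 95.7% | +4% |
| 92.2 / 92.2 | 97.8% | +19% |
| 75 / 90 (assumed; difference -15) | 95.0% | 0% |
| 83.6 / 60 (60 assumed) | 96.0% | +5% |
| 95 / 95 (assumed) | 99.1% | +36% |
| 10 / 10 (assumed) | 97.0% | +12% |
| 60 / 10 (assumed) | 97.9% | +18% |

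The inverted interval covers 94.9% to 95.3% in every row. At n = 144 the fixed-null results are much the same: 95.8% at 83.6/83.6, 97.9% at 92.2/92.2 and 99.1% at 95/95. Over a grid of rates from 5% to 95% in both arms at n = 129, the lowest fixed-null coverage is 94.4%, so the interval is never materially too narrow.

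**Primary decision.** Concluding non-inferiority from the lower limit of the inverted interval, with the plain FM variance, disagrees with the FM test at -15% in 0 of 130² = 16,900 outcomes at n = 129 and 0 of 145² = 21,025 at n = 144.

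**The case against.** The premise is inferred. SAP wording is often redundant, and if the sponsor meant full inversion there is no numerical defect. That stands, and it limits confidence in the size of the effect. The phrase would still be ambiguous to a programmer.

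The SAP says that these intervals are descriptive, and counts by arm will be tabulated, so a reader could rebuild any interval. That limits the consequence. It does not make an interval labelled 95% that covers 98% well specified.

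At the planning rate the effect is negligible: 9.3 against 9.2 points. The largest figure built from document rates puts the upper phase 2 limit for TAK-385 into both arms and into other windows. Even there the cost is 0.8 points of half-width (7.7 against 6.9). This stands, and it is why the point is minor.

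Direction matters. With 92.2% on leuprorelin and 83.6% on TAK-385, coverage is 95.7% rather than 97.3%, and at 75/90 it is 95.0%. So high rates alone do not produce the excess. Nor is it confined to extreme rates or very large gaps, because 88.6/83.6 already gives 96.5%. The change is gradual.

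One FM convention across all PBAC windows is also a defensible aim. The fix below can keep that.

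**Conclusion.** The point holds as a minor one. On the best-supported reading, the intervals in 7.8.2.1 and 7.8.3.4 are near nominal at the planning rate. They grow too wide as rates approach 0 or 1 and as the true difference departs from -15 points, more so when TAK-385 is the better arm. Among pairs built from document rates, coverage runs from 94.9% to 97.8% and width from 0% to 19% above Wald. At the assumed rates shown, coverage reaches 99.1% and the excess width 36%.

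A reader might infer three stronger things that the documents do not support:

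- That the margin phrase brings in a second, unadjusted non-inferiority test. The SAP rules out inferential use in both sections.
- That the intervals could produce a false claim. The error is conservative and no claim rests on them.
- That the primary conclusion is in doubt. SAP 7.8.1.1 does test at -15%, so a standard error evaluated there is the right one for that decision.

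The result assumes the fixed-null reading and 129 to 144 subjects per arm. Rates for these windows and for amenorrhea are not given, which is why a range is shown.

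**What to change.** In SAP 7.8.2.1 and 7.8.3.4, delete the reference to the -15% margin. State that the 95% interval is the score interval obtained by inverting the FM test, with the constrained proportions re-solved at each candidate difference.

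This has one small downside. If 7.8.1.1 keeps a fixed-null interval, the Weeks 6 to 12 interval will not be built in the same way as those for the other PBAC windows. Where one method is wanted throughout, the same inversion with the plain FM variance can also be used for the interval in 7.8.1.1, because it leaves the -15% decision identical to the FM test.

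The cost is SAP wording and a program option. It needs no new data, no more subjects and no protocol amendment, since Protocol 13.1.3 names no interval method for these proportions.

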7.8.2.2 Myoma Volumes and Uterine Volumes

Analysis Set: Full Analysis Set

Analysis

Variable(s): Myoma volumes
Uterine volumes

Visit: Baseline, Week 2, 4, 8, 12 and 24

Analytical

Method(s): For each variable, descriptive statistics will be provided for the observed values and the percent changes from baseline by treatment group for

each visit.

The mean differences in the percent changes from baseline between TAK-385 40 mg and leuprorelin group and the two-sided 95% confidence intervals will be provided.

7.8.2.3 Hemoglobin

Analysis Set: Full Analysis Set

Analysis

Variable(s): HGB (g/dL) [Min<= - <12, 12<= - <=Max]

Change from baseline on HGB [Min<= - <1, 1<= - <=Max]
(g/dL)

Subgroup(s): Oral iron preparation use at [Yes, No]
baseline

HGB at Baseline (g/dL) [Min<= - <12, 12<= - <=Max]

Visit: Baseline, Week 4, 8, 12, 16, 20, 24 and Follow-up

Analytical

Method(s): Summary statistics will be provided for the observed values and the changes from baseline by treatment group for each visit.

The mean differences in the change from baseline between TAK-385 40 mg and leuprorelin groups and the two-sided 95% confidence intervals will be provided for each visit.

For categorical variables, frequency will be summarized by treatment group for each visit. The differences in the percentage between TAK-385 40 mg and leuprorelin groups and the two-sided 95% confidence intervals will be provided for each visit.

Additionally, the above mentioned analysis will also be conducted for each subgroup.

7.8.2.4 NRS Score

Analysis Set: Full Analysis Set

Analysis

Variable(s): NRS score from Week 6 to 12

NRS score from Week 2 to 6
NRS score from Week 18 to 24
NRS score for 6 weeks before the final dose

Analytical

Method(s): For each variable, summary statistics will be provided by treatment group. Two-sided 95% confidence interval of the difference will be calculated between TAK-385 40 mg and leuprorelin group.

7.8.2.5 UFS-QOL Score

Analysis Set: Full Analysis Set

Analysis

Variable(s): Symptom Severity

Concern

Activities

Energy/Mood

Control

Self-consciousness

Sexual Function

HRQL Total

Visit: Baseline , Week 4, 8, 12, 16, 20, 24 and Follow-up

Analytical

Method(s): For each variable, descriptive statistics will be provided for the observed values and the changes from baseline by treatment group for each visit. The mean differences in the observed values between TAK-385 40 mg and leuprorelin group and the two-sided 95% confidence intervals will be provided for each visit.

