9.1.19 Pain Symptoms, Other Clinical Symptoms, and QOL

Pain symptoms are evaluated using the NRS score. The investigator or subinvestigator distributes the patient diary to consented subjects. Subjects fill out the patient diary every day from VISIT 1 to the day before VISIT 10 (or until early termination). Subjects record pain symptoms within 24 hours associated with uterine fibroids (NRS score), menstruation, and use of analgesics. If subjects use any analgesics for pain associated with uterine fibroids, they should record this fact in the patient diary along with the accompanying pain symptoms before use of analgesics. If there is anything unclear or insufficient description in the patient diary, queries may be made to the subject, and corrections to the patient diary are recorded by the subject in a change history that captures the old information, the new information, identification of the person making the correction and the date of the correction. If it is impossible to make queries to the subject at site visits, queries will be made to the subject with telephone calls or other means, and corrections to the patient diary are recorded by the investigator or subinvestigator in a change history that captures the old information, the new information, identification of the person making the correction and the date of the correction.

UFS-QOL score is used to evaluate other clinical symptoms and the QOL of subjects. The investigator or subinvestigator distributes the UFS-QOL questionnaire at VISITS 3, 5, 6, 7, 8, 9, 10 and 11 and has subjects fill it out before physical examination at site visit.

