7.1.1 Study Definitions

Duration of exposure to double-blind study drug (days) :

Date of last dose of double-blind study drug - date of first dose of double-blind study drug +
1

Double-blind study drug compliance (%) :

Number of TAK-385 blinded drugs taken/duration of exposure to TAK-385 blinded drug *
100 (rounded to 1 decimal places)

Disease duration (years):

((year of informed consent*12 + month of informed consent) -(year of first defined diagnosis of uterine fibroids*12 + month of first defined diagnosis of uterine fibroids))/12 (rounded to 1 decimal places)

Maximum drug holidays (days):

Maximum number of consecutive days on which the subject does not take the TAK-385 blinded drug for the treatment period

Total PBAC score from Week 6 to 12

Total PBAC score from Day 43 to earlier of Day 84 or Follow-up Day 3.

Similarly, Total PBAC score from Week 2 to 6 and from Week 18 to 24 will be defined as

those from Day 15 to earlier of Day 42 or Follow-up Day 3 and from Day 127 to earlier of Day 168 or Follow-up Day 3, respectively.

Total PBAC score for 6 weeks before the final dose of study drug

Total PBAC score for the last 42 days of the treatment

NRS score from Week 6 to 12

Average NRS score from Day 43 to earlier of Day 84 or Follow-up Day 3.

Similarly, NRS score from Week 2 to 6 and from Week 18 to 24 will be defined as average NRS score from Day 15 to earlier of Day 42 or Follow-up Day 3 and from Day 127 to earlier of Day 168 or Follow-up Day 3, respectively.

NRS score for 6 weeks before the final dose

Average NRS score for the last 42 days of the treatment

Total PBAC at baseline

Total PBAC score from first day of menstrual period confirmed at Visit 2 to a day prior to menstrual period confirmed at Visit 3

NRS score at baseline

Average NRS score from first day of menstrual period confirmed at Visit 2 to a day prior to menstrual period confirmed at Visit 3

Use of analgesic medications during the treatment from Week 6 to 12

((number of days with analgesic medications use between Day 43 and earlier of Day 84 or Follow-up Day 3)/(number of days with available data between Day 43 and earlier of Day 84 or Follow-up Day 3))*100 (rounded to 1 decimal places)

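### Secondary continuous comparisons ignore baselines already collected (a loss of precision only), and BMD has no planned between-arm estimate at all

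*SAP*

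**What the plan says.** **Patient-reported scales.** SAP 7.8.2.5 (UFS-QOL) specifies "The mean differences in the observed values between TAK-385 40 mg and leuprorelin group" with 95% intervals at each visit, and 7.8.3.3 (WPAI:GH) does the same. In both, change from baseline is summarised only within arm. For NRS, SAP 7.8.2.4 states: "Two-sided 95% confidence interval of the difference will be calculated between TAK-385 40 mg and leuprorelin group". The NRS variable is the raw average over each on-treatment window.

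**Hemoglobin and volumes.** SAP 7.8.2.3 uses "The mean differences in the change from baseline between TAK-385 40 mg and leuprorelin groups", and then adds: "Additionally, the above mentioned analysis will also be conducted for each subgroup". The subgroups are baseline HGB (below 12, or 12 g/dL and above) and oral iron use at baseline. For myoma and uterine volumes, SAP 7.8.2.2 uses "The mean differences in the percent changes from baseline between" the arms.

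**Interval method.** SAP 7.1 sets the default: "Confidence intervals for continuous variables will be calculated based on t-statistics". None of these sections names a model or covariate. The only analysis with a baseline covariate is the binomial regression for the primary endpoint in SAP 7.8.1.3.

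**Baselines available.** Protocol 9.1.19 says: "The investigator or subinvestigator distributes the UFS-QOL questionnaire at VISITS 3, 5, 6, 7, 8, 9, 10 and 11". VISIT 3 is Day 1. WPAI:GH is also collected at VISIT 3 (Protocol 9.3.2.1). SAP 7.1.1 derives a baseline NRS: "Average NRS score from first day of menstrual period confirmed at Visit 2" up to the day before the next period. SAP 7.4 tabulates it, but 7.8.2.4 does not use it.

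**BMD.** Protocol 13.1.5 and SAP 7.11.5.1 give by-arm descriptive statistics, frequencies and plots, and a T-score shift table. Neither plans a between-arm difference or interval.

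**The concern.** There are two separate points.

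First, when a baseline of the same variable predicts the follow-up value, adjusting for it narrows the interval for the treatment difference at almost no cost. Comparing raw follow-up values ignores that information. Comparing raw change uses it with a fixed slope of 1, which is seldom the best slope. The plan does one or the other for every continuous secondary comparison. Chance baseline imbalance is not a further harm, because the raw interval already allows for it.

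Second, BMD raises a comparative question that the planned output does not answer. Protocol 6.2.1 sets the 6-month treatment period partly to evaluate BMD against GnRH agonists, and the secondary objective (Protocol 5.1.2) compares 24-week safety with leuprorelin. The trial has a concurrent randomised leuprorelin arm, yet no difference or uncertainty is to be reported. WPAI:GH, an additional endpoint, gets a between-arm interval at every visit, while BMD, a named secondary safety endpoint, gets none. This is a missing estimate, not a precision issue.

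**Working it through.** **Sample size used.** SAP 6.0 gives 129 evaluable per arm. With the unpooled variance, n = (1.960 + 1.282)² × 2 × 0.836 × 0.164 / 0.15² = 10.51 × 0.2742 / 0.0225 = 128.1, rounded up to 129. Then 129/0.9 = 143.3, rounded up to 144 randomised. Both stated figures reproduce. I take n = 129 per arm below.

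**Assumed, because the documents are silent.** The baseline-to-follow-up correlation ρ, the ratio k of follow-up SD to baseline SD, and the SD of percent change in BMD.

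**Raw follow-up values (UFS-QOL, WPAI:GH, NRS).** In units of the follow-up SD:

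- Raw half-width = t(256) × √(2/n) = 1.969 × 0.1245 = 0.2452.
- ANCOVA half-width = t(255) × √[(1 − ρ²) × (2/n) × (1 + 1/(2n − 4))].

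| ρ | ANCOVA half-width | Change from raw |
|---|---|---|
| 0 | 0.2457 | 0.2% wider |
| 0.2 | 0.2407 | 1.8% narrower |
| 0.3 | 0.2344 | 4.4% narrower |
| 0.5 | 0.2128 | 13.2% narrower |
| 0.7 | 0.1755 | 28.4% narrower |

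A simulation of 20,000 trials with normal data gave the same percentages, with coverage of 0.948 to 0.954 for the raw and ANCOVA intervals.

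**Raw change (HGB).** With baseline SD = 1, the variance of change is k² + 1 − 2ρk and the ANCOVA variance is k²(1 − ρ²). The narrowing is 1 − √(ANCOVA variance / change variance), leaving out the degrees-of-freedom term of about 0.2%. For k = 1 and ρ = 0.5: 1 − √(0.75/1.00) = 13.4%.

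| k | ρ = 0.2 | ρ = 0.3 | ρ = 0.5 | ρ = 0.7 |
|---|---|---|---|---|
| 0.8 | 31.8% | 29.1% | 24.4% | 20.8% |
| 1.0 | 22.5% | 19.4% | 13.4% | 7.8% |
| 1.2 | 16.0% | 12.7% | 6.7% | 1.7% |

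Raw change therefore loses most where the correlation is low, the reverse of raw values. No figure is claimed for volumes.

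**Bias.** With complete data, simulation under no treatment effect (4,000 trials, 144 per arm) put the mean of every estimate within 0.005 SD of zero. At ρ = 0.5 the empirical standard errors were 0.119 (raw value), 0.120 (raw change) and 0.104 (adjusted).

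**BMD.** There is no planned interval to narrow. An unadjusted one would have half-width 0.2452 × SD of percent change: 0.49, 0.74 and 0.98 percentage points at SD 2, 3 and 4.

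**The case against.** The strongest reply is that the first point is a matter of preference. Protocol 13.1.3 asks for summary statistics and a 95% interval of the difference, and the SAP delivers that. Unadjusted differences with t-intervals are valid and transparent for untested endpoints. **This stands**: nothing in the plan is wrong or contrary to the protocol, and the case is for an improvement.

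The benefit may also be small. Entry requires a PBAC total of at least 120, while 83.6% are expected below 10 on treatment, so bleeding-related and pain scores may sit near the floor and correlate weakly with baseline. **This stands too**, and is why the table starts at ρ = 0. The simulation used normal data and does not vouch for coverage on floored scales. Each scale will have its own available n, but the percentage gains hardly depend on n.

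For HGB, the 2% lower end comes from stopping at ρ = 0.7. The gain vanishes when ρk = 1, for example k = 1.2 with ρ = 0.83. The planned strata already use baseline HGB and iron use, and a model with baseline HGB alone does not address iron. **That argues for keeping the strata**, but they give no pooled adjusted estimate.

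The statement that only precision is lost assumes complete data. SAP 7.1.4 uses available cases. In a hypothetical case with 10% dropout in each arm, random in one and confined to the highest-baseline fifth in the other, the unadjusted estimates shifted by 0.05 to 0.11 SD in magnitude at ρ = 0.3 to 0.7, and the adjusted ones by about 0. **This is a missing-data condition**, not an error in the intervals, and it does not favour the unadjusted analysis.

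On BMD, there is no hypothesis or margin, no other safety variable has a between-arm interval, and a reader can rebuild the unadjusted difference from n, mean and SD. **All true.** But BMD is the safety variable that Protocol 6.2.1 singles out for comparison, so the comparison should be stated in the planned output.

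**Conclusion.** The concern holds, in two parts of different kinds.

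1. The comparisons of UFS-QOL, WPAI:GH, NRS and HGB use no baseline covariate. The harm is lost precision only. How much is lost cannot be fixed from the documents: for raw values, from nothing at ρ = 0 to intervals that could be 28% narrower at ρ = 0.7, and for HGB change 2% to 32% over ρ 0.2 to 0.7 and k 0.8 to 1.2. The worst case of adjusting raw values is an interval 0.2% wider.
2. BMD has no planned between-arm estimate or interval, although the protocol poses the comparison. This is the more consequential part.

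The primary analysis, alpha and sample size are unaffected. The changes are worth making, but the trial's main conclusion does not depend on them. Confidence is medium, because every size rests on assumed correlations and SDs.

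**What to change.** - **SAP 7.8.2.4, 7.8.2.5, 7.8.3.3, and the pooled HGB change in 7.8.2.3:** estimate the between-arm difference and 95% interval by ANCOVA with treatment and the baseline of the same variable, labelled descriptive. Keep the planned descriptive summaries and the HGB strata.
- **SAP 7.8.2.2:** the same for percent change in volumes is optional.
- **SAP 7.11.5.1:** add the between-arm difference in percent change in BMD at Weeks 12 and 24 with its 95% interval, adjusted for baseline BMD and labelled descriptive. The gain from adjusting BMD has not been quantified; the essential addition is the estimate itself.

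**Cost:** SAP wording and programming, with no new data and no change to alpha or sample size. There are 89 models of one form: UFS-QOL 8 scales × 7 visits = 56, WPAI:GH 4 × 5 = 20, HGB 7, NRS 4 and BMD 2. The optional volumes add 2 × 5 = 10. Subjects without a baseline value drop out of the adjusted models, so their number should be reported beside each estimate.
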